1.3.2. Secondary Efficacy Analysis

The secondary endpoints from other questionnaires (MSAQ, SDQ, LTMSQ, STAI-6, PGI-S) will be analyzed in the same way as the primary endpoint. Other statistical methods may also be used as deemed appropriate. The details will be provided in the SAP.

1.4. Safety Data Analysis

1.4.1. Adverse Events

Adverse events will be recorded throughout the study and at early discontinuation. Adverse events and medical conditions will be coded using the Medical Dictionary for Regulatory Activities (MedDRA) coding dictionary. Treatment-emergent adverse events will be defined as those events, which are newly occurring or worsening from baseline. In all cases, only treatment emergent adverse events will be summarized.

Treatment-emergent adverse events will be summarized by presenting for each group the number and percentage of subjects having any treatment-emergent AE, having an AE in each body system, and having each individual AE. (Note: In any given category [e.g. body system] a subject will only be counted once.) Similar displays will be provided for prior (conditions

ending prior to the first dose of study medication) and current (conditions present while on study medication) medical conditions.

Adverse events will further be categorized by severity, relationship to study medication, and action taken. Other information collected will be listed, as appropriate. Any event starting more than 3 days after the final dose of study medication will be excluded from the above tables and only listed, unless the event caused discontinuation.

The proportions of subjects experiencing SAEs and AEs resulting in discontinuation from the study will also be summarized.

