VP-VLY-686-2401 Confidential

Motion Sifnos: A Randomized, Double-Blind, Placebo-Controlled Study to Investigate the Efficacy of Tradipitant in Subjects Affected by Motion Sickness during Travel

Document Type:	Clinical Study Protocol
Sponsor:	Vanda Pharmaceuticals Inc. [name]
Study Product:	tradipitant (VLY-686)
Protocol Number:	VP-VLY-686-2401
Study Phase:	II
IND Number:	141315
NCT Number:	NCT03772340

Date: 03 18 2019 **Status:** Final

Name of Sponsor/Company:

Vanda Pharmaceuticals Inc.

Name of Investigational Product:

Tradipitant/VLY-686

Name of Active Ingredient:

Tradipitant/VLY-686

Title of Study: Motion Sifnos: A randomized, double-blind, placebo-controlled study to investigate the efficacy of tradipitant in subjects affected by motion sickness during travel

Study Center(s): 1

Studied Period:	Phase of Development:
First subject enrolled: December 2018	Phase II
Estimated study duration: Four months	

Number of Subjects (planned): Approximately 150 affected subjects will be randomized and assigned to tradipitant 170 mg or placebo in a 1:1 ratio. Treatment assignments will be made according to a randomization schedule. Vehicle travel assessment will occur either in a motor vehicle (2A) or a boat (2B).

Diagnosis and Main Criteria for Inclusion: Adult males or females aged 18-75, inclusive, with a history of motion sickness who meet inclusion criteria.

Investigational Product, Dosage and Mode of Administration: Tradipitant 170 mg PO or placebo once approximately 60 minutes before entering the vehicle.

Duration of Treatment: If motor vehicle travel, one drive lasting approximately 120-240 minutes. If boat travel, one trip lasting approximately 90-300 minutes on the moving vessel.

Reference Therapy, Dosage and Mode of Administration: Placebo capsules will be provided in size and appearance identical to those containing tradipitant and will be administered orally.

Primary Objectives:

1. To assess the effects of tradipitant 170 mg on the symptoms of motion sickness during vehicle travel as measured by the MSSS.

Secondary Objectives:

- 1. To assess the effects of tradipitant 170 mg on the symptoms of motion sickness as measured by subjective parameter MSAQ.
- 2. To assess the effects of tradipitant 170 mg on the symptoms of motion sickness as measured by subjective parameter LTMSQ.

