- 3. To assess the effects of tradipitant 170 mg on the symptoms of motion sickness as measured by subjective parameter SDQ.
- 4. To assess the effects of tradipitant 170 mg on the symptoms of motion sickness as measured by subjective parameter PGI-S.
- 5. To assess the effects of tradipitant 170 mg on the symptoms of anxiety as measured by STAI-6.
- 6. To assess the safety and tolerability of a single oral dose of tradipitant 170 mg.

Overall Design: This is a randomized, double-blind placebo-controlled trial to investigate the efficacy and safety of a single 170 mg oral dose of tradipitant in motion sickness affected male and female subjects during vehicle travel.

The screening phase will consist of the subject taking the motion sickness eligibility questionnaire (MSEQ) to assess their susceptibility to motion sickness. Following this questionnaire, the subject will be interviewed to understand their history of motion sickness. If the subject meets pre-defined criteria as being eligible based on the motion sickness eligibility questionnaire and interview, they will proceed to the next step of a screening visit at a clinical site with a physician and simultaneously a lab visit for a blood draw. If the subject passes the medical visit screen and blood draw based on inclusion and exclusion criteria they will proceed to the evaluation phase.

Eligible subjects will be randomized 1:1 to tradipitant 170 mg or placebo. Eligible subjects will be instructed to take tradipitant 170 mg or placebo approximately 60 minutes prior to entering the vehicle. Vehicle travel assessment will occur either in a motor vehicle (2A) or boat (2B). Subjects will be driven on a pre-determined route for approximately 120-240 minutes during motor vehicle travel or approximately 90-300 minutes during boat travel. The MSSS questionnaire will be completed approximately every 30 minutes of vehicle travel and the STAI-6 will be completed at the beginning of vehicle travel, prior to drug administration.

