After the completion of the vehicle travel, subjects will complete several questionnaires including a motion sickness severity scale questionnaire (MSSS), a travel questionnaire for the subject to assess the likelihood of their travel experience to induce motion sickness based on experience scored from 1-9 (LTMSQ), a motion sickness assessment questionnaire (MSAQ), a questionnaire to record the duration of symptoms (SDQ), the 6-item Spielberger State-Trait Anxiety Inventory (STAI-6), and the Patient Global Impression of Severity Questionnaire (PGI-S). All questionnaires will be submitted for analysis. Subjects will then return for an EOS visit within 7 days of visit 2.

Statistical Methods: Motion sickness symptoms will be assessed by the MSSS questionnaire, with the other questionnaires serving as secondary endpoints. Motion sickness symptoms as measured by MSSS will be assessed by analysis of variance with the treatment group, vehicle, and site, if more than one site, as main effects. The primary efficacy analysis will be based on the ITT population. The statistical analyses will be detailed in the statistical analysis plan.

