1. STATISTICS

1.1. Sample Size and Accrual

A sample size of up to 75 subjects per arm (150 total) will provide around 86% power to detect a 0.8 point difference in motion sickness severity between Tradipitant and Placebo, with the standard deviation of motion sickness severity assumed to be around 1.6.

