1.2. Statistical Methods and Analysis Plan

1.2.1. General

This section describes the planned statistical analyses in general terms. A complete description of the methodology will be specified in a statistical analysis plan (SAP), which will be finalized prior to unblinding. Any changes in the statistical methods described in this protocol that occur prior to unblinding will be documented in the statistical analysis plan and will not require a protocol amendment.

Statistical hypothesis testing will be performed at two sided alpha level of 0.05. For continuous variables, population size (N for sample size and n for available data), the mean, the standard deviation (SD), the median, the minimum and maximum values will be tabulated. For categorical variables, population size and frequencies in each category will be tabulated.

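### Is the safety assessment weakened because adverse events starting more than 3 days after the single dose are listed rather than tabulated by arm?

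*Combined protocol and SAP*

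**What the plan says.** Section 1.4.1 collects adverse events for the whole study. It calls an event treatment-emergent if it is new or worse than at baseline, and sets no end date in that definition. Treatment-emergent events are tabulated by arm: any event, body system and individual event, then severity, relationship to drug and action taken. A subject counts once per category. Events whose onset lies beyond "3 days after the final dose of study medication will be excluded from the above tables and only listed, unless the event caused discontinuation". A later sentence in the same section plans a separate summary of serious events and of events leading to discontinuation.

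The synopsis fixes the timing. Dosing is "Tradipitant 170 mg PO or placebo once approximately 60 minutes before entering the vehicle". The longest exposure to travel is given under Duration of Treatment: "If boat travel, one trip lasting approximately 90-300 minutes on the moving vessel". On follow-up, Overall Design states: "Subjects will then return for an EOS visit within 7 days of visit 2". The sixth secondary objective is "To assess the safety and tolerability of a single oral dose of tradipitant 170 mg".

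Section 1.2.1 describes the analyses in general terms only and leaves the complete methodology to a SAP finalised before unblinding.

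**The concern.** The definition of a treatment-emergent event has no upper limit, yet the tables stop at an onset 3 days after dosing. Because there is only one dose, the final dose is also the first, so the clock starts at the only exposure. Follow-up can run to about day 7. A reader could conclude that up to 4 of 7 days are missing from the by-arm comparison, in a trial that names safety and tolerability as an objective.

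If that were a real loss, late-onset events could differ between arms without any table showing it. The reader would have to count them from listings for up to 75 subjects per arm.

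**Working it through.** The plan gives no figure on this point. Its only calculated figure is the power in section 1.1, which reproduces: 0.8 / (1.6 × √(2/75)) = 3.06, less 1.96 leaves 1.10, so power is 86.5% by the normal approximation (86.0% with the t distribution, 148 df), against about 86% stated. The adverse-event rule does not enter it.

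**Step 1: which events are affected.**

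| Kind of information | Treatment under the plan |
|---|---|
| Event starting by day 3, even if it lasts longer | In the by-arm tables, because the rule turns on onset |
| Later event causing discontinuation | In the by-arm tables, by the stated exception, and in the separate summary |
| Later serious event | In the separate summary, which follows the exclusion and carries no 3-day limit |
| Laboratory, vital-sign and ECG values (1.4.2 to 1.4.4) | Summarised by arm, no 3-day limit |
| Later non-serious event, no discontinuation | Recorded and listed, not tabulated |

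Only the last row is affected.

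**Step 2: how much follow-up time this is.** Assume visit 2 is the dosing day. The documents do not say so, but the travel assessments are labelled 2A and 2B and the dose is taken about an hour before boarding. For an end-of-study visit on day d, the listed-only share of time is max(0, d − 3)/d.

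| End-of-study day d | Listed-only days | Share |
|---|---|---|
| 3 or earlier | 0 | 0% |
| 4 | 1 | 1/4 = 25% |
| 5 | 2 | 2/5 = 40% |
| 6 | 3 | 3/6 = 50% |
| 7 | 4 | 4/7 = 57% |

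Check on the assumption: 60 min before boarding plus a 300 min boat trip is 360 min, or 0.25 day. Counting the 7 days from the end of travel gives at most (7.25 − 3)/7.25 = 59%, and 0.25/3.25 = 8% for a visit on day 3.

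**Step 3: from time to events.** The documents give no event rate, onset distribution or distribution of end-of-study days, so the number of events cannot be derived. If the onset rate does not rise after dosing, the mean rate after day 3 is no higher than the mean rate over the whole period. The share of events after day 3 is then at most (d − 3)/d. With onsets clustered near the dose, which is likely, it is well below that.

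The tables count subjects, once per category. A late event therefore adds to an incidence row only if that subject had no event in that row by day 3. For scale only, and as an assumption: if 1% to 10% of 75 subjects had such an event, 75 × 0.01 = 0.75 to 75 × 0.10 = 7.5 subjects per arm would have to be read from the listing.

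**Step 4: whether the tabulated comparison is valid.** The window is set before unblinding, depends only on onset date and applies equally to two randomised, double-blind arms. The tables answer a clear question: which events began within 3 days of the dose. The end-of-study visit may fall on any day up to 7, so a table running to that visit would mix follow-up of different lengths. The 3-day window is the same for every subject seen on day 3 or later.

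**The case for a change.** The strongest case for the concern is this. The discontinuation exception saves little after a single dose, because there is no further dosing to stop; a late event qualifies only if the subject leaves the study in the few days before the last visit. An abnormality found at an end-of-study visit on days 4 to 7 and reported as an adverse event with that onset would be left out of the adverse-event tables. Comparing arms needs counts by arm. The data are already collected and coded, and section 1.2.1 says that changes in methods made before unblinding "will be documented in the statistical analysis plan and will not require a protocol amendment".

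The facts in this argument stand: the rule is as described, the day arithmetic is right, and the text supplied describes no table through the end-of-study visit. The conclusion does not follow. An abnormal value found at the last visit still appears in the laboratory, vital-sign or ECG summaries. A late serious event reaches its own summary. No promise in the plan is broken, since no section undertakes to tabulate every event to the end of the study. Low cost would make an extra table easy to add, but does not make its absence an error. Repeating incidence, severity, relationship and action taken over a longer window would also mean several displays, and later background events could dilute a contrast expected near the dose.

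Two limits apply to both sides. The supplied text gives no reason for choosing 3 days, so that choice can be neither defended nor attacked on pharmacological grounds. And because section 1.2.1 leaves detail to the SAP, it cannot be established that a supplementary table is absent from the full plan.

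**Conclusion.** The concern does not hold. The 3-day rule is an openly stated onset window, equal in both arms, and it contradicts neither the treatment-emergent definition nor the safety objective. Followed as written, the plan gives a sound safety conclusion, and no bias is shown.

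The residue is a set of non-serious, late-starting events that do not cause discontinuation and that a reader finds in a listing instead of a table. It covers 0% to 57% of a subject's follow-up time (up to 59% with the 6-hour lag), depending on the end-of-study day. The number of events is not derivable from the documents and is probably small. The primary analysis and its power are unaffected.

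This rests on two readings: that visit 2 is the dosing day, and that the serious-event summary lies outside the cut-off because it follows the exclusion, which refers to the tables before it. The bound on the event share also assumes that the onset rate does not rise after dosing.

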1.4.2. Laboratory Data

The summary statistics of raw data (hematology and chemistry) and change from baseline values (means, medians, standard deviations, ranges) will be presented, as well as shift tables from baseline to post-baseline values using normal ranges. For urinalysis parameters, the number and percentage of subjects falling under each category of the test will be presented.

Clinical laboratory data will be summarized for each treatment group by presenting the proportions of subjects with clinically notable abnormalities. Clinically notable values (Appendix 20.1) will be identified according to the criteria identified in the FDA's "Supplementary Suggestions for Preparing an Integrated Summary of Safety Information in an Original NDA Submission and for Organizing Information in Periodic Safety Updates" (Revised 2-APR-87) provided by the FDA Division of Neuropharmacological Drug Products (DNDP).

1.4.3. Vital Signs and Body Measurements

Data from vital signs will be listed, clinically notable values as previously defined (Section 11.1.3) will be flagged, and any other information collected will be listed. Data will be summarized by group using mean change from baseline and proportions of subjects with values outside the normal range, and values that were clinically notable.

1.4.4. Electrocardiogram (ECG)

Results from the ECG will be listed for each subject. These data will also be summarized for each treatment group by presenting subjects with ECG abnormalities; shift tables; summary statistics of raw data and change from baseline values (means, medians, standard deviations, ranges).

1.5. Subgroup Analysis

Subgroup analysis (such as, gender, age, race etc.) for efficacy variables and safety variables may be conducted.

1.6. Interim Analysis

No interim analysis planned.

1.7. Deviations in Analysis from Statistical Plan and Other Issues

During the analysis and reporting process, any deviations from the statistical plan designed for this protocol will be described and justified in the final report.
